The Unified Parkinson's Disease Rating Scale (UPDRS)⁵² is an Investigator-used rating tool to follow the longitudinal course of Parkinson's disease. Every effort should be made by the Investigative sites to ensure that each subject is rated by the same rater throughout the subject's participation in the study. The UPDRS assessment will be performed by an approved, trained rater. To be qualified by the Sponsor and the rater vendor, all raters must have participated in the Rater Training and have a current valid Rater Certificate.

The UPDRS is made up of the following sections:

- Part I – Mentation, Behavior, and Mood
- Part II – Activities of Daily Living

- Part III – Motor Examination
- Part IV – Complications of Therapy (including dyskinesias)
- Part V – Modified Hoehn and Yahr Staging

Some sections require multiple grades assigned to each extremity. UPDRS total score ranges from 0 to 176, with 176 representing the worst (total) disability, and 0 no disability. Additionally, Questions 32, 33, and 34 of the UPDRS will be totaled to evaluate dyskinesias.

During Visit 1 the UPDRS Part III will be done during practically defined "Off" time and best "On" time. The practically defined "Off" time UPDRS will be done in the morning prior to the subject taking their first daily dose of anti-PD medication. The best "On" time rating should be done approximately 1 to 2 hours post any morning dose of study drug or PD medications but prior to lunch. If possible, the UPDRS should be done at the same time of day throughout the trial. The "Off" time UPDRS will only be done during Screening; at all other times a complete UPDRS (Parts 1 through 5) will be done during "On" time.

The UPDRS will be obtained at the times indicated in [Table 3](#).

Health Outcome Measurements

Clinical Global Impression of Change (CGI-C)

The CGI-C is a clinician's rating scale for assessing Global Improvement or Change. The CGI-C rates improvement by 7 categories: very much improved, much improved, minimally improved, no change, minimally worse, much worse, very much worse. Proportion of responders who had at least "minimally improved" in CGI-C ratings will be assessed.

A qualified rater will administer the CGI-C to the subject at the times indicated in [Table 3](#).

Patients' Global Impression of Change (PGIC)

The PGIC⁵³ is a 7-point response scale. The subject will be asked by the Investigator or qualified designee to rate their change in status using the following 7-point scale:

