9.3 Additional Efficacy Analyses

Secondary Analysis of the Primary Efficacy Variables

Analysis of covariance (ANCOVA) analyses will be carried out on change from baseline to final NMSS total score and change from baseline to final PDSS-2 total score. The ANCOVA model will contain treatment and country as the main effects and baseline score as the covariate. Sensitivity analyses will be carried out on the above variables with the same ANCOVA model using all randomized subjects. In this analysis, Baseline

Observation Carried Forward (BLOCF) will be applied to subjects who do not have post-randomization assessment of NMSS or PDSS-2.

Analysis of Secondary Efficacy Variables

The MMRM model, and the descriptive statistic summary described for the NMSS and PDSS-2 total score will also be used to evaluate the change from baseline in each of the following efficacy endpoints:

- UPDRS Part II score
- Parkinson's Disease Questionnaire-8 (PDQ-8) summary index
- NMSS domain scores
- PDSS-2 domain scores
- UPDRS total score, Part I score, Part III score, Part IV score
- Parkinson Anxiety Scale (PAS) total and subscale scores
- Geriatric Depression Scale (GDS-15)
- King's PD Pain Scale total and domain scores

For CGI-C and PGIC, an analysis of variance (ANOVA) model containing treatment and country as the main effects will be carried out.

UPDRS Part II score, CGI-C score and PDQ-8 summary index are key secondary endpoints. If both primary efficacy variables are statistically significant after adjusting for multiplicity, the Stepwise Gatekeeping Procedure will be utilized and the 3 key secondary endpoints will be tested using the Hochberg procedure with significance level of 0.05. Specifically, the following steps will be followed:

- If the largest of the 3 P values is ≤ 0.05 (i.e., all 3 P values are ≤ 0.05), all 3 key secondary endpoints are considered statistically significant.
- If the largest of the 3 P value is > 0.05 , then compare the middle P value with 0.025. The second and third key secondary endpoints are both statistically significant if the middle P value is ≤ 0.025 .

- If the largest of the 3 P value is > 0.05 and the middle P value is > 0.025 , then compare the smallest P value with 0.0167. If the smallest P value is ≤ 0.0167 , then the third key secondary endpoint is statistically significant. Otherwise, none of the 3 key secondary endpoints can be considered statistically significant.

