UPDRS: 42 questions, Part I (Questions 1 – 4), Part II (Questions 5 – 17), Part III (Questions 18 – 31), and Part IV (Questions 32 – 42). Questions 35 – 38 and 40 – 42 are 2-point (0 and 1), all other questions are 5-point (0 – 4).	Part I score	Sum of Questions 1 – 4. No missing answers will be imputed so Part I score will be missing if any of the answers are missing.	0 – 16/lower value desirable
	Part II score	Sum of Questions 5 – 17. Part II score will be calculated as long as at least 12 questions have been answered. If 1 answer is missing the Part II score will be calculated by multiplying the sum of questions answered by the ratio of the total number of Part II questions to the number of questions answered.	0 – 52/lower value desirable
	Part III score	Sum of Questions 18 – 31 with Questions 20 – 26 apply to multiple body parts, resulting in 27 answers total. Part III score will be calculated as long as at least 23 answers have been recorded. If 4 or fewer answers are missing the Part III score will be calculated by multiplying the sum of the answers provided by the ratio of the total number of Part III answers possible (27) to the number of answers provided.	0 – 108/lower value desirable
	Total score (Part I, II, III)	Sum of Part I, Part II, Part III scores. Will be missing if any one of Part I, Part II, Part III scores is missing.	0 – 176/lower value desirable

Table 7. Primary and Secondary Efficacy Variables, and Derivations (Continued)

Instrument	Efficacy Variable	Derivation	Range/Direction
UPDRS: 42 questions, Part I (Questions 1 – 4), Part II (Questions 5 – 17), Part III (Questions 18 – 31), and Part IV (Questions 32 – 42). Questions 35 – 38 and 40 – 42 are 2-point (0 and 1), all other questions are 5-point (0 – 4). (continued)	Part IV score	Sum of Questions 32 – 42. Part IV score will be calculated as long as at least 10 answers have been recorded. If 1 answer is missing the Part II score will be calculated by multiplying the sum of the answers provided by the ratio of the total number of Part III answers possible to the number of answers provided.	0 – 23/lower value desirable
CGI-C: 7-point scale (1 = very much improved, 2 = much improved, 3 = minimally improved, 4 = no change, 5 = minimally worse, 6 = much worse, 7 = very much worse)	CGI-C score	7-point score as collected	1 – 7/lower score desirable

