12.0 Summary of Changes

This SAP contains no change in analysis from the latest version of the protocol (Protocol Amendment 4).

The changes in this SAP from SAP V1.0 is: Per protocol amendments, subjects from South Korean/United States who complete the 26-week clinical study will have the option to enter an extension of the study. This SAP added the description for Extension Period analyses.

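### The UPDRS dyskinesia score promised in the protocol (Questions 32 to 34) is not derived or analysed anywhere; those items are analysed only as part of the mixed Part IV sum

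*Protocol*

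**What the plan says.** Protocol 5.3.1.1, under the UPDRS, describes the fourth section of the scale as "Part IV – Complications of Therapy (including dyskinesias" and then commits to a separate quantity: "Additionally, Questions 32, 33, and 34 of the UPDRS will be totaled to evaluate dyskinesias". The sentence carries no condition. SAP 4.5.3 sends the reader to Protocol 5.3.1.1 for the description of each health-outcome measure, UPDRS Parts I and II among them.

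The analysis sections are narrower:

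- Protocol 5.3.3 names the UPDRS total and section scores. Protocol 8.1.3.2 names Part II as key secondary, and the total and Parts I, III and IV as other secondary variables.
- SAP 9.3 has Part II and "UPDRS total score, Part I score, Part III score, Part IV score".
- SAP 9.4, Table 7, derives Part IV as "Sum of Questions 32 – 42. Part IV score will be calculated as long as at least 10 answers have been recorded". It has no row for Questions 32 to 34 alone.
- The SAP's UPDRS total covers Parts I to III only, so the Part IV items do not enter it.
- None of the safety analyses in SAP 10.1 to 10.8 uses the score.

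SAP 12.0 then states: "This SAP contains no change in analysis from the latest version of the protocol (Protocol Amendment 4".

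**The concern.** Motor symptoms and motor complications, measured by UPDRS Parts III and IV, form part of the secondary objective (Protocol 4.0). Dyskinesia is relevant in this trial. Limiting On time with troublesome dyskinesia is part of the definition of LCIG optimization (Protocol 5.1.2.2). Severe dyskinesia is named as a levodopa-related complication during titration (Protocol 5.5.1.2). Dyskinesia was also reported as an adverse event in the earlier open-label pool (Protocol 3.2, Table 1).

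No motor On/Off diary is among the efficacy variables; the Subject Dosing Diary records doses. The sum of Questions 32 to 34 is thus the only dedicated dyskinesia scale score that the protocol specifies. If the SAP is followed as written, no scale-based comparison of dyskinesia between arms is produced, and readers will have to judge dyskinesia from a score that mixes it with other complications.

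**Working it through.** **1. Reproduce the stated Part IV range.** Table 7 gives the item scoring as "Questions 35 – 38 and 40 – 42 are 2-point (0 and 1), all other questions are 5-point (0 – 4" and the Part IV range as "0 – 23/lower value desirable".

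- Five-point items within Questions 32 to 42 are 32, 33, 34 and 39: 4 × 4 = 16.
- Two-point items are 35 to 38 and 40 to 42: 7 × 1 = 7.
- Maximum = 16 + 7 = 23, which matches.

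**2. Split the range.**

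- Questions 32 to 34: 3 × 4 = 12, and 12/23 = 52%.
- The other eight items: 4 + 7 = 11, and 11/23 = 48%.

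**3. What this does to a comparison.** Write D for the between-arm difference in change on Questions 32 to 34, and R for the difference on the other eight items. The Part IV difference is D + R.

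- If R = 0, the Part IV difference equals D but carries the extra variability of eight items, unless the two sets of changes are negatively correlated strongly enough to cancel it. This is dilution.
- If R has the opposite sign, it offsets D. For example, D = +3 and R = −3 give 0. The scoring allows an offset of up to 11 points.
- If R has the same sign, Part IV can be more sensitive than D alone.

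The documents give no standard deviation, expected change or correlation for these items, so the probability of missing a real difference cannot be computed from them.

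**4. The other route, adverse events.** SAP 10.2.2 compares treatment-emergent events by preferred term with Fisher's exact test. In the earlier pool, dyskinesia was reported in 60/412 = 14.6%, with no comparator and a mean treatment duration of 854 days. As an illustration, assume that this rate carries over to LCIG at 44 per arm, with two-sided 5% tests:

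| Assumed OMT rate | Power |
|---|---|
| 2% | about 41% |
| 5% | about 20% |
| 10% | about 5% |

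The OMT rates are assumptions, and so is the carry-over of a long-term rate to 26 weeks. Protocol 6.1.1.1 also says that fluctuating PD symptoms during titration are not to be counted as adverse events, which narrows this route further.

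**The case against.** A reader might infer that the plan conceals a known harm of LCIG. The documents do not support that. Dyskinesia is neither among the Known or Potential Risks in Protocol 3.2 nor an adverse event of special interest in 6.1.1.3. The 14.6% is uncontrolled. Protocol 3.0 anticipates less dyskinesia with LCIG and reports a greater gain in On time without dyskinesia than with oral immediate-release levodopa-carbidopa. The omission could as easily obscure a benefit.

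A reader might also infer that Part IV must cancel a dyskinesia signal, with a calculable loss of power. That needs Questions 32 to 34 and the other eight items to move in opposite directions. The documents do not say what Questions 35 to 42 measure, and any power figure would rest on a chosen offset and chosen standard deviations.

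Three further objections have weight:

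- The inconsistency starts inside the protocol. On UPDRS variables the SAP follows Protocol 8.1.3.2, so its no-change statement conflicts with 5.3.1.1 and not with the protocol's statistical section.
- Dyskinesia is not invisible. Its adverse events are tabulated by preferred term, severity and relationship, and incidence is compared between arms.
- The protocol promises a total, not a test, so a descriptive summary would meet its literal wording.

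All of these limit how strongly the point can be put. None supplies the missing score.

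**Conclusion.** The point stands as an unfulfilled protocol commitment of moderate weight. The protocol says that a specific score will be formed, no analysis section forms it, and the SAP does not record its absence. Part IV is not an equivalent: 11 of its 23 points come from items that the protocol does not designate for dyskinesia, so a difference in either direction can be diluted or offset.

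That conclusion rests only on the SAP's scoring rules. How likely such masking is, and which way LCIG would move the score, cannot be settled from the documents. That the adverse-event comparison is a weak substitute rests on the assumed event rates shown and on the titration exclusion. The primary endpoints, key secondary endpoints, alpha and sample size are unaffected.

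**What to change.** 1. In SAP Table 7, add a row for a UPDRS dyskinesia score: the sum of Questions 32 to 34, range 0 to 12, lower values desirable. State a missing-item rule. The Part IV rule, which tolerates one missing answer in 11, should not be carried over by default, because one missing answer here removes 4 of 12 possible points.
2. In SAP 9.3, list the score as a non-key secondary variable outside the multiplicity procedure. Give descriptive summaries by arm and the same MMRM as the other UPDRS scores at Weeks 6, 12 and 26, reported beside Part IV.
3. Align Protocol 5.3.3 and 8.1.3.2 with 5.3.1.1, and record the addition in SAP 12.0.
4. In the same edit, correct the scaling sentence in the Part IV row of Table 7, which refers to Part II and Part III.

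The cost is SAP wording, one extra derived variable and table, and a short protocol alignment. The items are already collected whenever the UPDRS is done. Visits, sample size, alpha and clinical management do not change.

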5.3.1.2 Rater Requirements

All applicable clinical, safety, health outcome and cognition assessments will be administered only by individuals qualified by the Sponsor. Every effort must be made by the Investigative sites to ensure that each subject is rated by the same rater throughout the subject's participation in the study.

Prior to administration of respective scale(s), designated raters will be trained on and certified (if appropriate) in the use of all the scales used in this study. The objective of this certification/training is to ensure uniformity across sites in the administration and scoring of these assessments.

The Sponsor, in conjunction with the approved rater training vendor, if applicable, will determine the minimum rater qualifications for each of the rating scales. All raters must meet these qualifications prior to participation in the training process. The names and qualifications of all site personnel to be involved in rating scale administration will be submitted for approval upon site selection. The qualifications of the raters will be verified through the training vendor. Qualified raters will be trained and tested for competency and, if they meet established requirements, certified at the Investigator meeting. Individual exceptions to these requirements must be approved by the Sponsor via the training vendor if applicable.

Only those persons who have been trained as raters for this study may rate the subjects. Raters who cannot participate in the initial pre-study training or who become involved in the study at a later time will not be permitted to perform study ratings until they have satisfactorily completed an individualized training program designed by the rater training vendor if applicable, approved by AbbVie, and supervised by the Investigator or his/her designee. Raters may be reassessed periodically throughout the study.

Specific Rater Training Requirements

The UPDRS will be administered only by individuals qualified by the Sponsor and the rater training vendor. Prior to administration, designated raters (Investigator or an experienced and medically qualified study site designee [e.g., NP, PA, DO, MD, or PhD] assigned by the Investigator) will be certified in the use of the UPDRS. The objective of this certification/training is to ensure uniformity across sites in the administration and scoring of the scale.

The Sponsor, in conjunction with the rater training vendor, will determine the minimum rater qualifications for the rating scale. All raters must meet these qualifications prior to participation in the training process. The names and qualifications of all site personnel to be involved in the UPDRS, rating scale administration will be submitted for approval upon site selection. The qualifications of the raters will be verified through the rater training vendor. Qualified raters will be trained and tested for competency and, if they meet established requirements, will be certified. Individual exceptions to these requirements must be approved by the Sponsor via the rater training vendor.

Only those persons who have been trained and certified as raters for this study may rate the subjects. Raters who cannot participate in the initial pre-study certification/training or who become involved in the study at a later time will not be permitted to perform study ratings until they have satisfactorily completed an individualized certification/training program designed by the rater training vendor, approved by the Sponsor, and supervised by the Investigator or his/her designee. It is the responsibility of the Investigator to ensure the raters at his/her site are appropriately trained and certified to administer the selected rating scales. Raters will be reassessed periodically throughout the study.

Blinded Rater Training Requirements

The NMSS and PDSS-2 will be administered by blinded central raters on the respective scales at Randomization, V3. This will serve as the baseline for clinical assessment. They will also administer both scales at Weeks 6, 12, and 26.

It is required that only trained and certified specialists on movement disorders with previous experience using the NMSS scale in advanced PD patients will serve as blinded central raters and administer NMSS and PDSS-2. The blinded raters will not have access to the results of other study assessments or medical records for the subject and will not participate in the care or management of the subject. Each rating is based exclusively on an interview with the subject (and the subject's caregiver when available).

The blinded central rater will complete the NMSS and PDSS-2 at the times indicated in [Table 3](#) with the baseline assessment occurring at Screening Visit 3.

Rater Training Requirements for All Other Secondary Scales

Appropriate study site personnel will be trained on the use of all other secondary scales used in this study. Raters who become involved in the study after the Investigator's meeting will not be permitted to perform any study-specified ratings until they have satisfactorily completed the appropriate training program as designated by the Sponsor. It is the responsibility of the Investigator to ensure the raters at his/her site are appropriately trained to administer all rating scales.

5.3.1.3 Ancillary Support

Sites will be appropriately trained and provided support on the initiation and titration of LCIG prior to subject enrollment of the first subject at each site.

Duodopa Study Specialist (DSS)

The Sponsor may provide ancillary support to the study sites by utilizing a Duodopa Study Specialist (DSS) to provide additional training to the Investigator and site personnel. These DSS' training and consultation services will be similar to those provided in the previous Phase 3 program. DSS services and training are methods of support in the implementation of the LCIG administration system at clinical sites.

The functions of the DSS may include:

- Provide ongoing education and support to the site personnel (Investigator, gastroenterologist, study coordinators, research nurses, titration nurses and additional staff) throughout the enrollment period, initiation, titration and rest of the clinical trial
- Facilitate the implementation of the "Train the Trainer Model" by providing initial training to site staff. The Investigator or the appointed delegate may provide ongoing training to new staff.
- Educate the research site staff on medication, cassettes, basic/intermediate/advanced pump function, programming, troubleshooting, tubing, and stoma care
- Educate site personnel (e.g., nurses and physicians) in the proper handling, "Best Practices" for placement, and management of PEG-J tube
- Educate site personnel about Product Complaints and Adverse Events
- Meet local state and hospital/institution rules, laws, and regulations in regards to their role and responsibilities

5.3.2 Drug Concentration Measurements

No drug concentration measurements will be completed during the study.

5.3.3 Efficacy Variables

There will be two alternative primary efficacy variables.

- Change from baseline to Week 26 in NMSS total score
- Change from baseline to Week 26 in PDSS-2 total score

Secondary endpoints will consist of the following validated scales:

- UPDRS total score and section scores during "On" time
- PDQ-8 summary index and domain scores
- CGI-C

- PGIC
- PAS
- GDS-15
- King's PD Pain Scale

5.3.4 Safety Variables

Safety and tolerability over the course of the study will be assessed by the following measurements:

- Adverse event monitoring
- Neurological exams
- Clinical laboratory evaluations
- Electrocardiogram
- Vital signs and weight
- C-SSRS
- MIDI
- SAQ

5.3.5 Health Outcome Variables

The following measurements (already described in Section 5.3.3) are considered health outcomes:

- PDQ-8
- CGI-C
- UPDRS Parts I and II
- PGIC
- PAS
- GDS-15
- King's PD Pain Scale

5.4 Removal of Subjects from Therapy or Assessment

5.4.1 Discontinuation of Individual Subjects

Each subject has the right to withdraw from the study at any time. In addition, the Investigator may discontinue a subject from the study at any time if the Investigator considers it necessary for any reason, including the occurrence of an adverse event or noncompliance with the protocol. Subjects who withdraw from the study will not be replaced.

Subjects may develop adverse events or abnormalities in vital signs, ECGs, physical examinations, neurological examinations or laboratory determinations during their participation in the study. If these occur, the Investigator may discontinue a subject from the study if, in their clinical judgment, continued participation would result in undue risk or further worsening of the condition.

The following adverse events require Premature Discontinuation:

- Subjects who develop a melanoma during the course of the study should be discontinued from participation and referred for appropriate follow-up care
- Subjects who develop impulsive behavior that is clinically significant, in the judgment of the Investigator, should be discontinued from participation in the study and referred for appropriate follow-up care
- As indicated by answering yes to question 4 or 5 on the C-SSRS, subjects should be discontinued from participation in the study and referred for appropriate follow-up care
- Subjects who become pregnant should be discontinued from participation in the study and referred for appropriate follow-up care

In the event that a subject withdraws or is discontinued from the study after they have begun the PEG-J placement procedure, the assessments for a Premature Discontinuation Visit should be performed as soon as possible after discontinuation from the study.

If a subject is discontinued from the study with an ongoing adverse event or an unresolved laboratory result that is significantly outside of the reference range, the Investigator will attempt to provide follow-up until a satisfactory clinical resolution of the laboratory result or adverse event is achieved.

The Study Termination eCRF must be completed for all subjects who have entered the study (i.e., have signed the Informed Consent). Subjects dropping out prior to randomization will be considered Screen Failures and the reason for Screen Failure will be entered in the eCRF. In case of Premature Discontinuation of the subject after randomization, the primary reason for Premature Discontinuation will be entered in the eCRF.

